1. LIST OF ABBREVIATIONS

Abbreviation	Definition
mRCC	Metastatic Renal Cell Carcinoma
FSFV	First Subject First Visit
LSLV	Last Subject Last Visit
LSFV	Last Subject First Visit
SAE	Serious Adverse Event
NCI	National Cancer Institute
NIS	Non-Interventional Study
TKIs	Tyrosine Kinase Inhibitors
CTCAE	Common Terminology Criteria for Adverse Events
FKSI-15	The Functional Assessment of Cancer Therapy Kidney Symptom Index - 15
EQ5D-3L	EuroQoL-5 dimension – 3 level
FKSI-DRS	The Functional Assessment of Cancer Therapy Kidney Symptom Index—Disease-Related Symptoms
RECIST version 1.1	Response Evaluation Criteria in Solid Tumors
PFS	Progression-Free Survival
QoL	Quality of Life
ORR	Overall Response Rate
OS	Overall Survival
IFN	Interferon
KM	Kaplan Meier

SD	Standard Deviation
NUTS	Nomenclature D'unites Territoriales Statistiques
IRB	Institutional Review Board
WHO	World Health Organization
MedDRA	Medical Dictionary for Regulatory Activities
ADRs	Adverse Drug Reaction
e-CRF	Electronic Case Report Form

3. ABSTRACT

Observational Study Evaluating The Efficacy of Targeted Treatments Following Tyrosine Kinase Inhibitors in Metastatic Renal Cell Carcinoma Patients And Effects on Quality of Life: A National, Multicenter Study

Protocol Version: 2.1

Protocol Date: 09 March 2016

Main Author: PPD [REDACTED], Prof. at PPD [REDACTED]
PPD [REDACTED], MD, PhD at Pfizer

Background

Metastatic renal cell carcinoma (mRCC) is the most common malignant tumour of the kidneys. Targeted therapies, which were recently introduced in the treatment of mRCC, have become the standard treatment in these patients [1]. With improved survival rate and a tolerable side effect profile, Tyrosine Kinase Inhibitors (TKIs) have largely replaced conventional immunotherapies worldwide. [2-3]

In Turkey, due to reimbursement conditions defined by the authority, cytokine (interferon alpha) treatment is the standard treatment as first-line therapy [4].

Rationale

TKI therapy is used after interferon alpha in Turkey due to current reimbursement status. Therefore, the data on quality of life (QoL) from the pivotal studies with standard TKI treatment does not reflect the QoL status of patients treated with TKIs as second or third line treatment in Turkey. In this study, the clinical outcomes and the impact on quality of life of targeted treatments following TKIs will be explored. To our knowledge, since there is no similar reimbursement condition in the world placing IFN as the first line standard treatment, this will be the first study evaluating the QoL status with targeted therapies used as 3rd line treatment in mRCC patients.

Research Question and Objectives

Research Question:

There is no data available in the literature explaining the effect of targeted therapies used as 3rd line treatment following IFN and TKIs in metastatic renal cell carcinoma patients. Therefore, it is essential to understand health-related quality of life and efficacy of targeted therapies used as 3rd line treatment due to current reimbursement conditions in Turkey.

Primary Objective:

- Measurement of health-related quality of life with targeted therapy used as 3rd line treatment
- Overall response rate at the end of follow up
- Median progression free survival according to RECIST version 1.1

Secondary Objectives:

- Overall survival rate
- Effect of quality of life on prognosis.
- Adverse events during 3rd line targeted treatment according to CTCAE.4.03
- Dose modifications due to adverse events
- Correlation between efficacy (overall response rate at month 12 and median PFS) and dose modifications due to adverse events
- Correlation between efficacy (overall response rate at month 12 and median PFS) and blood pressure

Study Design

This is a multi-center, national, non-interventional/observational study. It has been defined according to the NUTS (Nomenclature of Territorial Units for Statistics: Nomenclature d'unités Territoriales Statistiques, French) criteria, which is a regional classification, created in order to reduce interregional disparities in socio-economic analysis of the regions, and to produce data comparable to that of the European Union (EU). Turkey has been divided into 12 NUTS regions depending on the economic, social, cultural, and geographical aspects, and the population size. In this study, patients with metastatic renal cell carcinoma from centers in 12 NUTS regions of Turkey will be included, who meet the inclusion criteria. In this study, approximately 152 patients planned to be recruited in 12 months and followed-up for 12 months. Additionally, every patient will be followed-up once for survival follow-up in order to assess the overall survival before the site close out visit. Survival follow-up will be performed via telephone visit or site visit if exist.

Study Population

Metastatic renal cell carcinoma patients under 3rd line targeted therapy following 1st line interferon alpha and 2nd line TKI. All patients will be ≥ 18 years old and have signed the informed consent document.

Variables

Age, gender, height, weight, and vital signs such as blood pressure

Socio-demographic characteristics

ECOG performance status

Concomitant diseases and medication

Medical history

Histopathological findings

Type of the surgical procedure

Treatment history and current treatment information

Metastatic features

MSKCC risk factors

Laboratory findings

The quality of life questionnaire (FKSI-15, EQ5D-3L, FKSI-DRS) on each visit.

Blood pressure diary

Other treatment during follow-up, if any, the dose and the duration

Side effects (treatment of the side effects, interruption of the treatment, dose reduction, dose-elevation)

PFS, OS and ORR evaluation during 3rd, 6th, 9th and 12th months performed according to RECIST version 1.1, additionally, every patient will be followed-up once for survival follow-up in order to assess the overall survival before the site close out visit. Survival follow-up will be performed via telephone visit or site visit if exist.

ORR: The best overall response is the best response recorded from the start of the study treatment until the end of treatment taking into account any requirement for confirmation. The patient's best overall response assignment will depend on the findings of both target and non-target disease and will also take into consideration the appearance of new lesions. Furthermore, depending on the nature of the study and the protocol requirements, it may also require confirmatory measurement.

PFS: The length of time during and after the treatment of a disease, that a patient lives with the disease but it does not get worse. In a clinical trial, measuring the progression-free survival is one way to see how well a new treatment works.

OS: 1 year Overall Survival (OS), defined as the time from the start of 3rd line treatment until death or 1 year due to any cause (measured at the end of follow-up).

Data Sources

The source of the data will be the electronic or the written patient records of the participating centers. The patient's data can be accessed through a patient file. In the centers, both systems can be used in conjunction. The data can be accessed using both systems.

Sample Size

This is a multi-center, national, non-interventional/observational study. In this study, patients with metastatic renal cell carcinoma who meet the inclusion criteria will be included from centers in 12 NUTS regions of Turkey. Since this is a non-interventional observational study, there is no specific follow-up protocol. In this study, approximately 152 patients will be evaluated.

According to Turkish Statistical Institute data at the end of 2013 population of Turkey is approximately 80 million [5]. In the project of Turkey Association of Cancer Research Control which was named Cancer Record and Incidence shows that cancer incidence is 100-150 in 100.000 [6] and 2% of all new cancers are renal cell carcinoma [7]. There would be 1800 new RCC patients in 1 year, and according to the OS of the disease, there would be 4000 RCC patients in Turkey. 15% of these are metastatic at the time of diagnosis and 30-40% of these are metastatic after a period of a time [8]. Presuming that there are 1800 patients with metastatic renal carcinoma in Turkey, the minimum sample size with 7,6 confidence interval, 95% confidence level and 80% power was calculated as 152.

Data Analysis

Data Analysis:

Statistical analyses will be primarily of explorative and descriptive nature. Patients who received at least one dose of 3rd line therapy and have sufficient information whether they had an adverse event or not will be valid for safety analysis. Patients who received at least one dose of 3rd line therapy and have any information regarding efficacy of therapy will be valid for intent-to-treat efficacy analysis.

Demographic data, baseline characteristics, diagnosis and prior treatment of RCC, concomitant diseases, and concomitant medication will be described with summary statistics such as mean, SD, minimum, 1, 5, 25, 75, 95, 99 percent quartiles, median, maximum for continuous variables, and category counts and frequencies (percentages) for categorical variables. Concomitant diseases on the case report form correspond to MedDRA terms. Concomitant medication will be coded using WHO's drug dictionary.

Descriptive summaries of Kaplan-Meier (KM) estimates (including number of failed, number censored, 25th and 75th percentiles with respective 95% confidence level and median with 95% Confidence level) and KM curves will be presented for time-to-event efficacy variables (PFS, TTP, time to treatment failure). Mean, SD, minimum, 1, 5, 25, 75, 95, 99 percent quartiles, median, maximum will be produced for duration of treatment. Category counts and frequencies (percentages) will be calculated for tumor status at different visits and general subjective rating of efficacy of 3rd line therapy from the treating physician.

Adverse events will be summarized using the CTCAE.4.03 coding system. Event rates for single adverse events will be calculated based on the total number of patients valid for safety. Adverse events will be categorized according to relation, seriousness, CTCAE grade (version 4.03), and discontinuation of therapy, action taken and outcome. Special attention will be paid to serious adverse events and unexpected or unlisted ADRs.

Category counts and frequencies (percentages) will be calculated for overall tolerability.

Since the enrollment is after the initiation of the treatment, some information will be collected and analyzed retrospectively.

The best overall response is the best response recorded from the start of the study treatment until the end of treatment taking into account any requirement for confirmation.

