7. RESEARCH QUESTION AND OBJECTIVES

Research Question:

In this study, different from other studies in the literature, the data will be collected to observe the quality of life and efficacy after first line interferon alpha and second line TKI treatments.

Primary Objective:

- Measurement of health-related quality of life with targeted therapy used as 3rd line.
- Overall response rate at the end of follow up
- Median progression free survival according to RECIST version 1.1

Secondary Objectives:

- Overall survival rate
- Effect of quality of life on prognosis.
- Adverse events during 3rd line targeted treatment according to CTCAE.4.03
- Dose modifications due to adverse events
- Correlation between efficacy (overall response rate at month 12 and median PFS) and dose modifications due to adverse events
- Correlation between efficacy (overall response rate at month 12 and median PFS) and blood pressure

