8. RESEARCH METHODS

8.1. Study design

This is a multi-center post-marketing observational study. It has been defined according to the NUTS (Nomenclature of Territorial Units for Statistics: Nomenclature d'unités Territoriales Statistiques, French) criteria, which is a regional classification, created in order to reduce interregional disparities in socio-economic analysis of the regions, and to produce data comparable to that of the European Union (EU). Turkey has been divided into 12 NUTS regions depending on the economic, social, cultural, and geographical aspects, and the population size. In this study, patients with metastatic renal cell carcinoma from centers in 12 NUTS regions of Turkey will be included, who meet the inclusion criteria. Since this is a non-interventional observational study, there is no specific follow-up protocol. In this study, approximately 152 patients planned to be recruited in a year and followed-up 12 months.

This is a multi-center post-marketing observational study. In this study, patients with metastatic renal cell carcinoma from centers in 12 NUTS regions of Turkey will be included,

who meet the inclusion criteria. Since this is a non-interventional observational study, there is no specific follow-up protocol.

Presuming that there are 1800 patients with metastatic renal carcinoma in Turkey, the minimum sample size was calculated as 152.

There will be a total of 25 centers in various cities of Turkey.

The centers will consist of medical oncology clinics.

In this study, the patient follow-up period is 12 months. Each patient will be followed up to 5 times; the data will be collected at baseline, the 3rd, 6th, 9th and 12th months according to the routine practice. Additionally, every patient will be followed-up once for survival follow-up in order to assess the overall survival before the site close out visit. Survival follow-up will be performed via telephone visit or site visit if exist.

Because of the observational nature of the study, there is no predefined treatment protocol. The participating physician will continue to treat the patients at his/her own discretion. Frequency of visits will be continued per physician's preference.

The patients will be asked to fill in the quality of life questionnaire (FKSI-15, EQ5D-3L, FKSI-DRS) on each visit.

The assessment of the side effects will be based on the "Common Terminology Criteria for Adverse Events". The CTCAE V.4.03 will be used.

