8.3. Variables

The outcome variables for the objective(s) are time to treatment failure (from start of treatment to progression or permanent discontinuation), overall survival (from start of treatment to the date of last follow up or death), therapeutic response to therapy based on response evaluation criteria in solid tumors (RECIST version 1.1), and safety (type, incidence, severity of adverse events graded by the National Cancer Institute [NCI] CTCAE V.4.03)

Variable	Role	Data source(s)	Operational definition
Age, gender, height, weight, blood pressure, socio-demographic characteristics	Baseline characteristic	Medical Records	
Concomitant diseases	Baseline Characteristic	Medical Records	
Medication	Baseline Characteristic	Medical Records	
Histopathological findings	Baseline Characteristic	Medical Records / Pathology Reports	
Surgical Operations	Baseline Characteristic	Medical Records	
The cytokine (interferon alpha) usage in the first-line treatment, TKI usage in the 2 nd line treatment and the dosage and the duration of the treatment	Baseline Characteristic	Medical Records	
Metastatic features	Baseline Characteristic	Medical Records	
MSKCC risk factors	Baseline Characteristic Follow-up Characteristic	Medical Records	
3 rd line treatment	Baseline Characteristic Follow-up Characteristic	Medical Records	

	Close-out Characteristic		
The performance score before the second and third-line treatment		Medical Records	
The quality of life questionnaire (FKSI-15, EQ5D-3L, FKSI-DRS) on each visit	Baseline Characteristic Follow-up Characteristic Close –out Characteristic	Patient interview	
Blood pressure		Patient diary	
Other treatment during follow-up, if any, the dose and the duration	Follow-up Characteristic	Medical Records	
Treatment of the side effects, interruption of the treatment, dose reduction, dose-elevation	Baseline Characteristic Follow-up Characteristic	Medical Records	
Duration of PFS, OS and ORR	Follow-up Characteristic Close-out Characteristic	Medical Records	

Schedule Procedure	Initial visit	Follow-up 3.month	Follow-up 6.month	Follow-up 9.month	Follow-up 12.month	Survival Follow-up
Demographic data	X					
Histopathological Findigs	X					
Medical history	X					
Previous therapy of mRCC	X					
MSKCC Risk Factors	X	X	X	X	X	
Surgical Operations	X					
Metastases Information	X					
FKSI-15, EQ5D-3L, FKSI-DRS Questionnaire	X	X	X	X	X	
Evaluation of PFS,OS and ORR		X	X	X	X	
Concomitant medication	X	X	X	X	X	
Visit date	X	X	X	X	X	

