8.7. Data analysis

Statistical analyses will be primarily of explorative and descriptive nature. All issues concerning patient validity, data consistency checks, permissible data modifications will be described in detail in the Data Management Plan.

Patients who took at least one dose of 3rd line treatment and have sufficient information whether they had an adverse event or not will be valid for safety analysis. Patients who took at least one dose of 3rd line treatment and have any information regarding efficacy of 3rd line treatment will be valid for intent-to-treat efficacy analysis.

Demographic data, baseline characteristics, diagnosis and prior treatment of RCC, concomitant diseases, and concomitant medication will be described with summary statistics such as mean, SD, minimum, 1, 5, 25, 75, 95, 99 percent quartiles, median, maximum for continuous variables, and category counts and frequencies (percentages) for

categorical variables. Concomitant diseases on the case report form correspond to MedDRA terms. Concomitant medication will be coded using WHO's drug dictionary.

Descriptive summaries of Kaplan-Meier (KM) estimates (including number of failed, number censored, 25th and 75th percentiles with respective 95% confidence level and median with 95% confidence level) and KM curves will be presented for time-to-event efficacy variables (PFS, TTP, time to treatment failure). Mean, SD, minimum, 1, 5, 25, 75, 95, 99 percent quartiles, median, maximum will be produced for duration of TKI treatment. Category counts and frequencies (percentages) will be calculated for tumor status at different visits and general subjective rating of efficacy of TKI from the treating physician.

Adverse events will be summarized using the MedDRA and the CTCAE coding system. Event rates for single adverse events will be calculated based on the total number of patients valid for safety. Adverse events will be categorized according to relation, seriousness, CTCAE grade (version 4.03), and discontinuation of therapy, action taken and outcome. Serious adverse events and unexpected or unlisted ADRs will be evaluated separately.

Category counts and frequencies (percentages) will be calculated for overall tolerability.

The factors, which might have impacted the duration of treatment, will be studied by retrospectively.

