9.4. Ethical Conduct of the Study

The study will be conducted in accordance with legal and regulatory requirements, as well as with scientific purpose, value and rigor and follow generally accepted research practices described in Guidelines for Good Pharmacoepidemiology Practices (GPP) issued by the International Society for Pharmacoepidemiology (ISPE), Good Epidemiological Practice (GEP) guidelines issued by the International Epidemiological Association (IEA).

This is a non-interventional study where the 3rd line targeted treatment are prescribed in the usual manner in accordance with the terms of the marketing authorization. There is no assignment of a patient to a particular therapeutic strategy, the treatment decision falls within current practice and the prescription of the medicines is clearly separated from the decision to include the patient in the study. No additional diagnostic or monitoring process is required for participation or during the study. Epidemiological methods shall be used for the analysis of the collected data.

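### The primary median PFS is to be estimated by ordinary Kaplan-Meier with no rule for dating progression and no allowance for interval censoring, so it will tend to be overstated, by an amount that depends on how often patients are actually scanned.

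*Combined protocol and SAP*

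**What the plan says.** Section 7 lists "Median progression free survival according to RECIST version 1.1" among the three primary objectives. The Abstract (Variables) gives the timing: "PFS, OS and ORR evaluation during 3rd, 6th, 9th and 12th months performed according to RECIST version 1.1". The schedule table in section 8.3 agrees: the row "Evaluation of PFS,OS and ORR" and the separate row for response assessment are marked at the four follow-up visits and not at the initial visit.

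Section 8.7 plans Kaplan-Meier summaries and curves for PFS, including the "median with 95% confidence level". It names no interval-censored method and no sensitivity analysis. PFS is described in lay terms in the Abstract and as enrolment to progression or death in section 8.1. In the section 8.3 variable table, the operational-definition cell for "Duration of PFS, OS and ORR" is empty and the source is medical records. No section says whether progression is dated at the scan or at the study visit, asks for the last progression-free assessment date, or gives a censoring rule for PFS.

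Other text qualifies the timetable. In section 8.1, "the data will be collected at baseline, the 3rd, 6th, 9th and 12th months according to the routine practice" and "Frequency of visits will be continued per physician's preference". In section 9.4, "No additional diagnostic or monitoring process is required for participation or during the study".

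**The concern.** RECIST progression is seen at an assessment, but it happened at some time between that assessment and the one before. Kaplan-Meier takes the date it is given as the event time. If that date is when progression was found, every progression is placed late, the curve shifts to the right, and the median rises. The confidence interval reflects sampling error among 152 patients but not the width of the assessment gap.

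The Abstract says that no data exist for this third-line setting, so the reported median may become a reference figure. A reader who sets it beside a study with more frequent assessment would see a difference that comes partly from the timetable.

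**Working it through.** **Inputs from the documents.** N = 152 (section 8.5); assessments at months 3, 6, 9 and 12 (Abstract, section 8.3); 12 months of follow-up (section 8.1); Kaplan-Meier median (section 8.7); death counts as a PFS event (section 8.1).

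**Assumed, because the documents give no value.** Exponential PFS, true medians of 3 to 10 months, the share of events that are deaths (0%, 15% or 30%, dated exactly), and the routine scan interval.

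**The plan's own figure.** There is no expected median PFS to reproduce. The only computed design figure is N, and it reproduces as a precision calculation for a proportion, with p = 0.5 assumed: n0 = 1.96² × 0.25 / 0.076² = 166.3, then 166.3 / (1 + 165.3/1800) = 152.3. It does not concern PFS.

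**By hand, progression dated at 3-monthly visits, no deaths.** With true median m, the proportion progression-free at time t is 0.5^(t/m). The Kaplan-Meier median is the first visit at which the observed proportion is 0.5 or less.

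- m = 4: 0.5^(3/4) = 0.595 at month 3 and 0.5^(6/4) = 0.354 at month 6, so the median reads 6.
- m = 5: 0.660 at month 3 and 0.435 at month 6, so it reads 6.
- m = 7: 0.552 at month 6 and 0.410 at month 9, so it usually reads 9. The standard error at month 6 is √(0.552 × 0.448 / 152) = 0.040, so 0.552 lies 0.052/0.040 = 1.3 standard errors above 0.5, and about one study in ten would read 6.

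Simulation agrees. In 400 runs each, a true 4 gave 6 in 399; a true 5 gave 6 in 385 and 9 in 15; a true 7 gave 9 in 358 and 6 in 36.

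**Mean error in the Kaplan-Meier median (150 to 300 runs per cell).**

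| Dating of progression | Deaths | True medians | Mean bias (months) |
|---|---|---|---|
| Next 3-monthly visit | 0% | 3–10 | +1.0 to +2.1 |
| Next 3-monthly visit | 15% | 3–10 | +0.8 to +1.8 |
| Next 3-monthly visit | 30% | 3–10 | +0.5 to +1.7 |
| 3-monthly visit with 0.5-month SD and 0–1 month origin shift | 15% | 3–10 | +1.2 to +1.6 |
| Scan date, irregular gaps of 1.5–3 months | 15% | 3–9 | +0.8 to +1.1 |
| Scan date, every 2 months | 15% | 3–10 | +0.5 to +1.0 |
| Scan date, every month | 15% | 3–10 | +0.2 to +0.5 |
| Exact event date | all patterns | 3–10 | −0.3 to +0.1 |

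At a true median of 10, up to 5% of runs did not reach a median by month 12 and are left out of the mean.

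**Interval coverage, no deaths.** With exact dates, the 95% interval (log-log) contained the true median in 94–97% of runs. On the strict 3-month grid it did so in 34%, 2% and 79% (true 4, 5 and 7). With scan dates at irregular 1.5–3 month gaps the figures were 9%, 43% and 67%.

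**Does the remedy work?** Using the same 3-monthly data with 15% exactly dated deaths and true medians of 3 to 9, an interval-censored Weibull fit had mean bias of −0.04 to +0.05 months. Kaplan-Meier on interval midpoints had −0.3 to +0.4. The exponential is a special case of the Weibull, so this test favours the Weibull fit.

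**The case against.** The strongest reply is that months 3 to 12 are data-collection points, not a scan schedule. The study follows routine practice, physicians choose visit frequency, no added diagnostics are required, and PFS comes from medical records. Scans may be more frequent than 3-monthly, and their dates may be on file. The eCRF is not among the documents, so its date fields cannot be judged. This stands, and it rules out three stronger readings that a reader might infer:

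- **That disease is assessed only at the four listed months, or that the plan dates progression at the study visit.** Neither is stated; the plan is silent on dating.
- **That the median must fall on 3, 6, 9 or 12.** This needs exact visit timing and few deaths. With 30% exactly dated deaths it held in only 38–95% of runs, and with visit spread and an origin shift in none.
- **That the bias is 1 to 2 months whatever happens.** It is smaller with frequent scans or many deaths. In a single study on a strict grid, the timetable alone can add anything from 0 to 3 months.

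It is also fair that section 8.7 calls the analysis descriptive, that no comparison with outside PFS data is planned, and that detection delay affects any PFS based on periodic assessment.

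What the reply does not remove is the direction of the error. A scan date is still a detection date, and ordinary Kaplan-Meier on scan dates still overstated the median in every pattern tried. That dates may be on file is also no rule for 25 centres to apply alike.

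**Conclusion.** The point holds in conditional form. The stated method overstates the primary median PFS, and its confidence interval leaves out the uncertainty from the assessment gap. On average the overstatement is about 1 to 2 months if progression is dated at 3-monthly visits (about 0.5 to 1.7 with 30% exactly dated deaths), about 1 month with routine scans every 1.5 to 3 months, and 0.2 to 0.5 months with monthly scans. These sizes rest on the assumed exponential shape, true medians and death shares, and the coverage figures apply only to the two scan patterns simulated. The direction does not depend on those choices.

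A reader might also infer that a study conclusion is invalidated. The documents do not support that: PFS is a single-cohort descriptive estimate, and section 8.5 states no hypothesis. What is affected is the reported median, its interval and any comparison with outside figures. This is a worthwhile, inexpensive improvement.

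**What to change.** 1. State in sections 8.3 and 8.7 that progression is dated at the tumour assessment that shows it, not at the study visit where it is entered.
2. Record on the eCRF, where not already captured, the date of each routine tumour assessment, including the last one without progression.
3. Beside the Kaplan-Meier median, report an interval-censored median with 95% CI, with each progression placed between the last progression-free assessment and the one showing progression, and deaths at their exact dates. Turnbull assumes no shape, but may locate the median only within an interval if assessments cluster. Weibull gives a point value at the price of a shape assumption. Name the choice in advance.
4. Describe the observed gaps between assessments, so that readers can judge the size of the effect.

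No extra scans are needed and care does not change. The cost is a few date fields, a little programming and probably a less favourable median. Dates not collected as the study runs may be hard to recover later.

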8.2. Setting

Metastatic renal cell carcinoma patients who progressed after a TKI therapy following a cytokine (interferon alpha) treatment will be enrolled to the study. The study enrollment period is 12 months And the follow-up period of a patient is 12 months.The study period is 36 months.

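### Third-line treatment duration is summarised as if every patient had a stop date, so among enrolled patients the mean, SD, upper percentiles and maximum are too low or mark the follow-up limit

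*Combined protocol and SAP*

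**What the plan says.** In section 3 (Abstract, Data Analysis), Kaplan-Meier estimates with numbers failed and censored "will be presented for time-to-event efficacy variables (PFS, TTP, time to treatment failure". Treatment duration is not in that list. The next sentence gives it an ordinary summary: "Mean, SD, minimum, 1, 5, 25, 75, 95, 99 percent quartiles, median, maximum will be produced for duration of treatment".

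Section 8.7 repeats the pair of sentences, but there the second ends "median, maximum will be produced for duration of TKI treatment". It adds: "The factors, which might have impacted the duration of treatment, will be studied by retrospectively". No method is named for that analysis.

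On follow-up, section 8.2 states: "The study enrollment period is 12 months And the follow-up period of a patient is 12 months". The schedule in section 8.3 records third-line treatment at the initial visit and at months 3, 6, 9 and 12. The later survival contact records survival status only. Section 8.2.1 admits patients who have been on third-line drug for up to one month, and section 9.2 lets patients withdraw at any time. Nothing says how a patient who is still on drug, withdrawn or lost enters the duration summary.

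**The concern.** A patient still taking third-line drug at the last visit has no stop date. The true duration is known only to exceed the observed time. The plan recognises this for the three neighbouring time-to-event variables but not for treatment duration.

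Followed as written, the analyst has two options: enter the last visit as if treatment had stopped there, or leave out patients without a stop date. The first cuts the longest-treated patients to the length of follow-up. The second removes them. Either way, the mean for the enrolled patients is too low. The requested 95th and 99th percentiles and the maximum would then say more about when observation ended than about how long patients stayed on treatment.

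**Working it through.** **The plan's own figure.** The documents state no treatment duration and no share still on drug at month 12, so there is nothing on this point to reproduce. The sample size of 152 does reproduce as a precision calculation (p = 0.5 assumed): 1.96² × 0.25 / 0.076² = 166.3, and with a population of 1800, 166.3 / (1 + 165.3/1800) = 152.3. It does not depend on treatment duration. It is used below only to turn shares into patient counts.

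**Limit of observation.** Up to 1 month on drug at entry (8.2.1) plus 12 months of follow-up, taken as running from enrolment (8.2), gives a longest observable duration of about 12 to 13 months.

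**Closed form.** Assume exponential time to stopping with median m, everyone followed to month 12 and no entry delay. With λ = ln 2 / m:

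- share on drug at month 12 = exp(−12λ)
- true mean = 1/λ
- mean with ongoing patients cut at month 12 = (1 − exp(−12λ))/λ, so the relative bias is −exp(−12λ)
- true 95th percentile = ln(20)/λ

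| Median (months) | On drug at 12 | Mean, cut v true | Bias | True 95th percentile |
|---|---|---|---|---|
| 4 | 12.5% | 5.0 v 5.8 | −12.5% | 17 |
| 6 | 25% | 6.5 v 8.7 | −25% | 26 |
| 8 | 35% | 7.5 v 11.5 | −35% | 35 |

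**With delayed entry.** This simulation assumes entry uniform over the first month on drug, observation ending 12 months after entry, and patients who stop before entry not enrolled. Truth is the uncensored duration of the enrolled patients. Exponential case:

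| Median (months) | On drug at end (of 152) | Mean, cut v true | Mean if ongoing dropped | 75th, cut v true | 95th, cut v true |
|---|---|---|---|---|---|
| 4 | 12.5% (19) | 5.5 v 6.3 | 4.5 | 8.5 v 8.5 | 12.6 v 17.7 |
| 6 | 25% (38) | 7.0 v 9.2 | 5.2 | 12.1 v 12.5 | 12.8 v 26.5 |
| 8 | 35% (54) | 8.0 v 12.0 | 5.5 | 12.3 v 16.5 | 12.9 v 35.2 |
| 10 | 44% (66) | 8.6 v 14.9 | 5.7 | 12.4 v 20.5 | 12.9 v 43.7 |

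The SD falls too: 3.9 v 5.8 months at a median of 4.

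**Wider assumptions.** Weibull shapes 0.8, 1.0 and 1.3 with medians of 3 to 10 months leave 1% to 46% on drug. The cut mean is too low by between 0.5% (shape 1.3, median 3: 3.89 v 3.91) and 55% (shape 0.8, median 10: 8.58 v 19.02). The reported 95th percentile sits at about 12 to 13 months in every case except shape 1.3 with median 3, where only 1.3% are ongoing.

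**Which summaries are affected.** If ongoing patients are cut at the last visit, a percentile is wrong only when it falls among them. Under the exponential, percentile q lies beyond a limit L when m > L·ln 2 / (−ln(1 − q)). For L = 12 to 13 months:

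- 99th percentile: median above about 1.8 to 2.0 months
- 95th: above about 2.8 to 3.0 months
- 75th: above about 6.0 to 6.5 months, that is, about 25% or more ongoing
- median: only if 50% or more are ongoing, which no scenario reached (highest 46%)

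If ongoing patients are dropped, the median moves as well: at an exponential median of 6 it is 4.6 months against 6.5 in the enrolled patients.

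These thresholds concern patients censored at the end of follow-up. Withdrawal or loss while on drug was not modelled. If last contact were then entered as the stop date, lower percentiles could also be pulled down.

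**The case against.** **Time to treatment failure already has Kaplan-Meier.** Section 8.3 defines it as "time to treatment failure (from start of treatment to progression or permanent discontinuation". A measure close to time on drug will therefore be reported with censoring handled, which reduces the harm. It does not remove it. Time to treatment failure also ends at progression, and section 8.1 leaves treatment to the physician, so a patient may stay on drug afterwards.

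**Section 8.7 may mean another line of treatment.** Patients enter after progressing on a TKI (8.2), and section 8.3 lists the duration of second-line TKI as a baseline characteristic. On that reading the duration is complete at entry and nothing is censored. This objection stands for section 8.7 until the wording is settled. The matching passage in section 3 favours the third line, because its next sentence refers to the physician's rating of third-line therapy. The point on section 3 stands either way.

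**The summary is descriptive.** Treatment duration is neither a primary nor a secondary objective, and the analysis is declared mainly exploratory. That limits the importance of the point, but a descriptive mean can still be wrong.

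**Stronger readings that the documents do not support.**

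- A reader might infer that the whole summary, median included, is understated. With patients cut at the last visit and early losses set aside, the median is sound below 50% ongoing.
- A reader might infer understatement for everyone who starts third-line treatment. Patients who stop before enrolment cannot enter, and this pushes the other way: at an exponential median of 3 months the cut mean is 4.5 months against 4.3 for all starters.
- A reader might infer that the analysis of factors affecting duration will be biased. The tests listed in section 8.6 do not handle censoring, but no text assigns them, or any method, to that analysis.

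**Conclusion.** The point holds for third-line treatment duration in section 3, and for section 8.7 if its sentence also means third line. The stated method treats a right-censored variable as complete. Among enrolled patients it gives a mean and SD that are too low, and in nearly all scenarios tried a 95th percentile, 99th percentile and maximum at about 12 to 13 months whatever the true values. The effects on the 75th percentile and median are conditional, as set out above.

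The size rests on an unknown share still on drug at month 12. Under exponential medians of 4 to 8 months the mean is low by about 12% to 35%. The wider range, under 1% to about 55%, is the fairer statement of what is known. The point is worth correcting because the change is cheap. It does not threaten the primary objectives or the sample size.

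**What to change.** 1. Reconcile the two sentences in sections 3 and 8.7 on which line of treatment is meant. If second-line TKI duration is also wanted, list it separately as a baseline variable with an ordinary summary.
2. Summarise third-line treatment duration by Kaplan-Meier from treatment start. The event is permanent stop for any reason, including death. Patients on drug are censored at the last known on-treatment date, and each patient joins the risk set at enrolment (delayed entry).
3. Report the number ongoing, the median and quartiles with 95% confidence intervals where reached and otherwise as not reached, and the percentage on drug at months 3, 6, 9 and 12.
4. Label any ordinary summary that is kept as observed duration within follow-up.
5. Name log-rank or Cox methods, on the same variable and with the same delayed entry, for the factors affecting duration.

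**Cost.** New wording in two sections, with no added visits or patients. The case report form should be checked for start, permanent-stop and last on-treatment dates. The definition of time to treatment failure implies a stop date, but the variable table gives no operational definition for third-line treatment. Upper percentiles may be not reached, and the first weeks of the curve may be unstable while few patients have entered the risk set.
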